7 STATISTICAL METHODS & DETERMINATION OF SAMPLE SIZE

7.1 Statistical and Analytical Plans

There will be only 1 database lock and 1 analysis after all subjects complete or prematurely discontinue from the study. The statistical methods provided in this protocol will be focused on primary efficacy analysis. Complete and specific details of the statistical analysis will be described in the Statistical Analysis Plan (SAP).

7.2 Definition for Analysis Populations

The full analysis set (FAS) is composed of all randomized subjects who have received at least 1 dose of study drug in this study. The data from the FAS will be presented by the treatment group assigned at the time of randomization, even if a subject does not receive the correct treatment or does not follow the protocol until completion. The FAS will be used for all baseline and efficacy analyses.

The Safety Analysis Set includes all randomized subjects who received at least 1 dose of study drug. The data from the safety analysis set will be presented by the treatment actually received regardless of which treatment group was assigned at the time of randomization. If a subject takes more than 1 treatment, the subject will be analyzed in the safety analysis set as taking the treatment to which she is randomized. All safety analyses will be performed based on Safety Analysis Set.

7.3 Statistical Analyses for Efficacy

Primary Efficacy Analysis

The primary efficacy analysis will be based on the FAS, and the primary endpoint will be the proportion of responders meeting the following conditions:

- MBL volume < 80 mL at the Final Month (the last 28 days of treatment)
- $\geq 50\%$ reduction in MBL volume from Baseline to Final Month (the last 28 days of treatment)

Subjects whose primary reason for prematurely discontinuing study drug is "lack of efficacy," or "requires surgery or invasive intervention for treatment of uterine fibroids" will be considered as non-responders.

The primary endpoint will be analyzed using a logistic regression model including treatment as the main effect and baseline MBL volume as a covariate. Missing Final Month MBL volume will be imputed using multiple imputation. For subjects who prematurely discontinue the Treatment Period prior to Month 6, the Final Month (the last 28 days prior to and including the last dose date) will be used in the primary analysis.

Additional Efficacy Analyses

Details on other efficacy analyses are provided in the SAP.

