## **8.0 Efficacy Analyses**

### **8.1 General Considerations**

All efficacy analyses will be conducted in the FAS Population. All tests will be 2-sided at an alpha level of 0.05.

Unless otherwise specified, categorical data will be summarized by frequency and percentage; descriptive summaries of continuous data will display the mean, SD, median, minimum, and maximum.

For continuous variables, when the analyses of change and/or percent change from Baseline to post-baseline visit(s) are performed, the within-group change from Baseline to each applicable visit will be summarized by treatment group with the mean, SD (or SE), and 95% Confidence Intervals (CIs). The between-group differences will be summarized with the mean, SE, 95% CIs, and P value when applicable. At each post-baseline visit, the Baseline mean and post-baseline visit mean will be calculated for all subjects with baseline and post-baseline value at that visit by treatment group.

Final Month is defined as the last 28 days prior to and including the last dose day.

Unless otherwise specified, there is no hypotheses testing for efficacy endpoints in the Post-Treatment Follow-up Period.

Information regarding corresponding statistical methods for analyses and any additional statistical measures required for a specific variable/endpoint will be provided in relevant sections.

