#### **8.3.3 Primary Efficacy Analysis**

The primary analysis of the primary endpoint will be performed using the full analysis set population.

If a subject has missing observed Final Month MBL volume, the Final Month MBL volume will be imputed using multiple imputation as described in Section 8.2.

The primary analysis of the primary efficacy endpoint with multiple imputation will be carried out in the following steps:

1. **Multiple Imputation:** 30 "complete" datasets of monthly MBL volume from Month 1 to Month 6 will be generated using SAS PROC MI as described above. The following covariates will be used in the imputation model:
  - a. Baseline MBL volume

- b. Randomized treatment group
  - c. Baseline hemoglobin
  - d. MBL volume in prior months
  - e. Age of the subject at Baseline
2. **Impute Final Month MBL Volume:** In each of the 30 generated datasets, subject's missing Final Month MBL volume will be imputed using the MBL volume from the "complete" dataset with Month 1 – 6 MBL volume by looking at the corresponding month of the last dose day using analysis time window. Subjects whose last dose day are the same as Study Day 1 will have their Final Month MBL volume imputed using their Month 1 MBL volume.
3. **Impute Responder Status:** The responder status (yes/no) will be derived from "complete" (observed or imputed) Final Month MBL volume, using the criteria as described in Section 8.3.1. Subjects whose primary reason for prematurely discontinuing study drug is "lack of efficacy," or "requires surgery or invasive intervention for treatment of uterine fibroids" will be considered as non-responders.
4. **Analysis:** Each of the 30 imputed datasets will be analyzed separately using a logistic regression model including treatment as the main effect and Baseline MBL volume as a covariate to compare the elagolix treatment group to placebo.
5. **Pooling:** Estimates of the proportions of responders in each treatment group and the difference between the proportions from the 30 imputed datasets obtained from step 3 will be combined into one overall result using PROC MIANALYZE in SAS.

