### 8.3.4 Additional Analyses of the Primary Efficacy Endpoint(s)

#### Sensitivity Analyses

The sensitivity analyses for the primary endpoint use different approaches to handle prematurely discontinued subjects, missing Final Month MBL volume, and AH data from validated versus unvalidated products.

The analysis set used for sensitivity analyses is the full analysis set. Each of the following sensitivity analyses for the primary endpoint will be performed using a logistic regression model including treatment as the main effect and Baseline MBL volume as a covariate to compare the elagolix treatment group to placebo.

Unless otherwise specified, subjects whose primary reason for prematurely discontinuing study drug is "lack of efficacy," or "requires surgery or invasive intervention for treatment of uterine fibroids" will be considered as non-responders.

1. The primary analysis will be repeated with all subjects categorized as responders/non-responders based on observed or imputed MBL volume data only (without taking into account their reasons for premature discontinuation of study drug). Multiple imputation will be performed the same way as in the primary analysis.
2. Non-responder imputation (NRI): All subjects who have missing Final Month MBL volume will be considered as non-responders. No multiple imputation will be performed.
3. Observed cases: The primary analysis will be repeated with the observed Final Month MBL volume. Subjects who have missing Final Month MBL volume will be excluded from this analysis.
4. The primary analysis will be repeated using the total MBL volume collected from validated products only. All subjects will be categorized as responders/non-responders in the same manner as done in the primary analysis (i.e., using the

multiple imputation described in Section 8.3.3) with the exception that all AH data (including that for Baseline MBL volume) will be based on the total MBL volume collected from validated products only.

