### **Additional Analyses**

Each of the two response criteria that is a component of the primary endpoint, i.e., (1) MBL volume of < 80 mL at the Final Month; and (2) 50% or greater reduction in MBL volume from Baseline to the Final Month will be analyzed separately in the same way as for the primary analysis. Baseline and Final Month MBL volumes obtained for the primary analysis via MI will be used. The number and percentage of subjects meeting each criterion at the Final Month will be summarized by treatment group. The comparison between the elagolix treatment group and placebo will be made using a logistic regression model including treatment as the main effect and Baseline MBL volume as a covariate.

Besides the method in the primary analysis, the number and percentage of subjects meeting each criterion at the Final Month will also be analyzed in the same way as in each sensitivity analysis for the primary endpoint.

The number and percentage of subjects satisfying either (1) MBL volume < 80 mL, or (2) 50% or greater reduction in MBL volume from Baseline, or both will be summarized for every 28-day interval by treatment group based on observed MBL volume. This summary will also be provided at Final Month of the Treatment Period for subjects who prematurely discontinue study drug due to "lack of efficacy," or "requires surgery or invasive intervention for treatment of uterine fibroids" as the primary reason. Cross-tabulation of the two bleeding criteria above for each 28-day interval in the Treatment Period will be provided by treatment group based on observed MBL volume.

Plots will be provided by treatment group using the MBL volume data for the primary analysis (after multiple imputation):

- Proportion of responders at Final Month.

Additional supportive analysis of the primary efficacy endpoint using Bayesian historical borrowing may be explored. Historical data of placebo subjects from AbbVie M12-815 and M12-817 studies may be incorporated in the analysis based on the consistency and similarity between historical placebo data and current placebo data. Details of the historical borrowing method are provided in [Appendix D](#).

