### **Amenorrhea**

The number and percentage of subjects who achieve amenorrhea will be calculated for each treatment group. The amenorrhea analysis includes subjects on study drug for at least 38 days. For each subject, amenorrhea at the Final Month is defined as having 0 days of bleeding or spotting during the last 28 days prior to and including the last dose day, with the interval starting at or beyond Study Day 11. If a subject does not have evaluable AH data during the last 28 days and no bleeding or spotting or "There was no visible blood on the sanitary products" is indicated on UBQ, then she is considered amenorrheic. The denominator will be the number of subjects with at least 38 days on study drug and having an amenorrhea status at the Final Month. The number and percentage of subjects with amenorrhea at Final Month will be summarized by treatment group and compared between the elagolix treatment group and placebo using the Miettinen-Nurminen (M-N) method.

Time to amenorrhea is defined as the number of days from the first study drug dose date to the day a subject achieves amenorrhea (i.e., the day a subject achieves amenorrhea – the first study drug dose date + 1). For a subject who achieves amenorrhea, the day she achieves amenorrhea is defined as the next day of the last bleeding/spotting day during the Treatment Period. The median, Q1, and Q3 of time to amenorrhea will be calculated for subjects who achieve amenorrhea using Kaplan-Meier method.

In the monthly analysis of bleeding for amenorrhea, the numerator will be the number of subjects on treatment who do not bleed or have spotting during the specified time window specified in [Table 1](#) (but may have begun bleeding or spotting thereafter) and the denominator will be the number of subjects on study drug for the full window and having an amenorrhea status for that month.

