### **PGIC on Menstrual Bleeding Questionnaire**

For PGIC on menstrual bleeding (PGIC – MB), the number and percentage of subjects in each response category will be summarized at each applicable visit by treatment group. Missing data will not be imputed. No statistical tests will be performed.

For PGIC – MB, the response categories of "Very Much Improved" and "Much Improved" will be combined and the remaining five categories of the PGIC scale will be combined and labeled "Otherwise." The number and percentage of subjects with response of (a) "Very Much Improved" or "Much Improved," and (b) "Otherwise" will be summarized at each applicable visit by treatment group. Comparisons will be made using the Miettinen-Nurminen (M-N) method for each applicable visit in the Treatment Period.

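### The primary logistic regression has no named test, no stated pooled treatment effect and no rule for an arm with no responders, which has an 18.5% chance in the placebo arm on the plan's own inputs

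*Protocol*

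**What the plan says.** Protocol 7.3 gives the primary method in one sentence: "The primary endpoint will be analyzed using a logistic regression model including treatment as the main effect and baseline MBL volume as a covariate". SAP 8.3.3 step 4 applies it after imputation: "Each of the 30 imputed datasets will be analyzed separately using a logistic regression model including treatment as the main effect", with baseline MBL as covariate, in order to compare elagolix with placebo. SAP 8.1 adds only "All tests will be 2-sided at an alpha level of 0.05".

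Step 3 of SAP 8.3.3 derives each subject's yes/no responder status. Step 5 pools the arm proportions, and "the difference between the proportions from the 30 imputed datasets obtained from step 3 will be combined into one overall result using PROC MIANALYZE". It mentions no coefficient, odds ratio, standard error or p-value.

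The sensitivity analyses in SAP 8.3.4 use the same model: "Each of the following sensitivity analyses for the primary endpoint will be performed using a logistic regression model including treatment as the main effect". The two components of the endpoint "will be analyzed separately in the same way as for the primary analysis".

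For other binary endpoints the SAP does name a method. Amenorrhea is "compared between the elagolix treatment group and placebo using the Miettinen-Nurminen (M-N) method", suppression of bleeding is handled likewise, and for dichotomised PGIC-MB "Comparisons will be made using the Miettinen-Nurminen (M-N) method for each applicable visit in the Treatment Period".

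Protocol 7.7 and SAP 2.4 claim at least 80% power with 32 elagolix and 16 placebo subjects, response rates of 55% and 10%, and two-sided alpha 0.05.

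**The concern.** A primary analysis needs one named test statistic, a rule for combining it over the imputed datasets, and a rule for data in which it cannot be computed. The plan has the model but none of the three.

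The third gap is a practical one. The placebo arm is small and its expected response is low, so a placebo arm with no responders is quite likely. Treatment then separates the outcomes whatever the covariate does. The ordinary maximum-likelihood treatment coefficient runs to infinity and its Wald test has no power. Such a trial may carry the strongest evidence of benefit and still have no usable primary result. The Miettinen-Nurminen method, named for the other binary endpoints, still works with zero responders.

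The candidate tests differ in power and in type I error. If the choice is left until the data are seen, it becomes data-driven.

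**Working it through.** **Inputs.** From Protocol 7.7 and SAP 2.4: 32 and 16 subjects, 55% and 10% response, two-sided 0.05. From SAP Appendix D: historical placebo rates of 7.4% and 10.2%, and about 90% of subjects with an observed endpoint (28:14).

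**1. The plan's own figure.** Let r = 2, d = 0.45 and the pooled rate be (0.10 + 2 × 0.55)/3 = 0.40. The two-proportion formula for the placebo arm is

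n = [1.96·√(3 × 0.40 × 0.60) + 0.842·√(2 × 0.10 × 0.90 + 0.55 × 0.45)]² / (2 × 0.45²) = 12.1, so 13.

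The continuity correction, (n/4)·[1 + √(1 + 6/(2n × 0.45))]², gives 15.2, so 16 placebo and 32 elagolix. The stated 48 reproduces, but from a formula that is not the planned logistic test.

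**2. Chance of no placebo responder.** This is (1 − p)^16.
- p = 10%: 0.9^16 = 18.5%
- p = 7.4%: 29.2%
- p = 10.2%: 17.9%
- p = 10% with only 14 placebo subjects observed: 0.9^14 = 22.9%

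**3. What each candidate test would deliver.** Exact enumeration of all outcomes at 32:16, with complete data and no covariate:

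| Test | Power, 55% vs 10% | Type I error, both arms 10% |
|---|---|---|
| Ordinary Wald, zero cell counted as non-significant | 71.9% | 1.3% |
| Likelihood ratio | 91.9% | 7.0% |
| Score / chi-square | 91.8% | 3.7% |
| Fisher | 86.5% | 2.2% |
| Firth, Wald (two standard-error formulas) | 85.2–87.6% | 1.5% |
| Firth, penalised likelihood ratio | 90.8% | 2.7% |
| Difference in proportions, unpooled variance | 94.5% | 8.4% |

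Given at least one placebo responder, Wald power is 0.7192/0.8147 = 88.3%. The shortfall below 80% therefore comes from the zero-responder case.

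**4. Does the covariate rescue it?** Simulation of the adjusted model used 4,000 runs per setting and an assumed log-odds ratio of 0 or −0.8 per SD of baseline MBL. Power was 71–74% for Wald and 93–94% for the likelihood ratio. With no placebo responder, Wald rejected in none of the runs and the likelihood ratio in all of them. Adjusted Firth Wald had 85–90% power and about 1.3% type I error at 10%. The adjusted Firth penalised likelihood ratio had about 91–94% and about 3%.

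**5. With imputation.** A simple imputation was assumed, not the SAP's MBL model: about 10% missing, responder status drawn within arm, 30 datasets, Rubin's rules. Pooled Firth Wald then has about 80–83% power and about 1.1–1.3% type I error at 10%. At least one of the 30 datasets has no placebo responder in about 22–23% of trials.

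**6. Behaviour at zero.** With 0/16 on placebo, two-sided p < 0.05 needs 12/32 elagolix responders under Firth Wald, and 7/32 under the score test or the Firth penalised likelihood ratio.

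**The case against.** The strongest reply is that the plan does assign the comparison to the logistic model. Step 4 is there to compare the arms, and step 5 can be read as descriptive output, with the reference to step 3 attached to the datasets rather than the estimates. That reading is fair. It leaves step 4 with no stated pooled result, which is the gap described here.

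Three stronger inferences are tempting, and the documents do not support them.

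- **The primary test has 8.4% type I error.** This needs the step 5 difference to be the hypothesis test and its variance to be unpooled. The SAP says neither. Even then the figure depends on the common rate: 3.4% at 5%, and about 7% at 10% with about 10% imputed.
- **The sample size is wrong.** It is not. Fisher, chi-square and score tests all exceed 80%, and so does Wald given at least one placebo responder.
- **The component analyses carry the same 18.5%.** They inherit the unnamed test. Each component is at least as easy to meet as the composite, so a zero placebo count is no more likely there; at an assumed 20% placebo rate it would be 0.8^16 = 2.8%.

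Step 5 also cites two sources on pooling, which were not available. The statement here is only that the SAP text gives no rule.

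Finally, Protocol Appendix E calls the study exploratory, and the Bayesian analysis in SAP Appendix D can handle a zero placebo count. But that analysis is supportive and optional, and the plan still states one primary hypothesis, a two-sided 0.05 level and a power figure.

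**Conclusion.** The point holds and should be fixed before unblinding. The primary test is unnamed, the model's treatment effect has no stated pooled result in the SAP text, and there is no rule for an arm with no responders. That event has an 18.5% chance in the placebo arm on the plan's inputs, and 17.9–29.2% over the two historical placebo rates.

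The unnamed test decides whether the power claim is met: 71.9% for the ordinary Wald test, against 86.5% or more for Fisher, score and likelihood-ratio tests. The 71.9% rests on complete data, no covariate, and counting separated fits as non-significant; adjusting for an assumed covariate effect moves it only to 71–74%.

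Confidence is high on the gap and on the 18.5%. It is lower on power under imputation, because a simple imputation stood in for the SAP's model.

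**What to change.** 1. **SAP 8.3.3 step 4 and the 8.3.4 analyses.** Keep the model (treatment, baseline MBL) but fit it by Firth penalised likelihood (FIRTH option in PROC LOGISTIC). The treatment estimate stays finite when an arm has no responders.
2. **SAP 8.3.3 step 5.** State that the penalised treatment log-odds ratio and its standard error from step 4 are combined by Rubin's rules in PROC MIANALYZE, and that the resulting two-sided p-value is the primary test. Report the pooled proportions and their difference alongside as descriptive.
3. **Analyses without imputation (NRI, observed cases).** Name the Firth penalised likelihood-ratio test. No pooling is needed there, and it does better than the Wald form (about 91% power, 2.7% type I error at 10%).
4. **Protocol 7.7 and SAP 2.4.** Name the test behind the 80% figure and say that it assumes complete data. Add that power is about 80–83% if about 10% of outcomes are imputed, under a simple imputation.

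The cost is one software option, a rewritten step 5 and a longer power sentence, with no extra patients. The statistical price is a conservative primary test (about 1.5% type I error at 10% on complete data), with less power than a score test (85–88% against 91.8%) and the higher hurdle at zero placebo responders shown above. A score or Miettinen-Nurminen primary test would also close the gap, but would need its own pooling rule, and Miettinen-Nurminen would drop the baseline MBL covariate.

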7.4 Statistical Analyses for Safety

Analysis of safety parameters will include the following:

- The number and percentage of subjects with AEs
- A summary of laboratory values

The full list of safety endpoints and corresponding analyses will be presented in the SAP.

7.5 Statistical Analyses for Pharmacokinetics/Pharmacodynamics

Plasma concentrations of elagolix and serum concentrations of estradiol will be listed for each subject by visit day and dose regimen, as applicable. Pharmacokinetic data may be combined with data from other studies in women and exposure-response analyses may be conducted as appropriate. For example, if PK exposures are estimated, analyses may be conducted to assess the relationship between PK parameters or estradiol concentrations and efficacy and safety responses. Additional analyses will be performed if useful and appropriate.

7.6 Overall Type I Error Control

No multiplicity adjustment is needed for this study as there is only 1 endpoint being analyzed and there is only 1 analysis of this endpoint.

7.7 Sample Size Determination

Approximately 48 subjects will be randomly assigned (in a 2:1 ratio) to receive either elagolix 150 mg QD (N = 32) or placebo (N = 16). The sample size will provide at least 80% power to detect a difference between the elagolix 150 mg QD group and the placebo group in the percentage of subjects meeting the primary endpoint on MBL at the Final Month of the placebo-controlled Treatment Period, with a final volume < 80 mL and an improvement of $\geq 50\%$ from Baseline, assuming response rates of 10% for the placebo group and 55% for the elagolix 150 mg QD group with a 2-sided $\alpha = 0.05$. The above sample size was calculated using nQuery Advanced 8.1.

